1.8.6. Risks From Combination Therapy

The combination of the immunotherapies epacadostat and pembrolizumab have the potential to precipitate more frequent, more severe, and/or new immune-related toxicities as compared with each individually. The addition of azacitidine, INCB057643, or INCB059872 to the epacadostat and pembrolizumab regimen may have the potential to increase irAEs due to their ability to re-express and up-regulate genes related to diverse immune pathways. The combination of azacitidine with pembrolizumab and epacadostat has been well-tolerated in Cohorts 1, 2A, 2B, and 3 with no DLTs observed to date in Part 1.

2- STUDY OBJECTIVES AND ENDPOINTS

2-L Study Objectives

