5.2.5.3. Storage

Bottles of tablets should be stored in a refrigerator and maintained at a temperature between 2°C and 8°C (36°F-46°F).

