5.4.1.1. Dose-Limiting Toxicity and Determination of Maximum Tolerated Dose

A DLT will be defined as the occurrence of any of the toxicities in Table 10 occurring up to and including Day 21 for Treatment Group A or Day 42 for Treatment Groups Band C. Only toxicities with a clear alternative explanation (eg, due to disease progression), transient (72 hours) abnormal laboratory values without associated clinically significant signs or symptoms based on investigator determination, irAEs of Grade 3 or higher that improve to Grade 1 or lower in < 5 days by appropriate care or with corticosteroid therapy can be deemed a non-DLT. All DLTs will be assessed by the investigator using the current CTCAE v4.03 criteria. Subjects who receive 2:75% doses of study drug (Treatment Group A: azacitidine [4 doses], epacadostat [32 doses], and pembrolizumab [1 dose]; Treatment Group B: INCB057643 [32 doses], epacadostat [32 doses], and pembrolizumab [1 dose]; Treatment Group C: INCB059872 [QD dosing, 32 doses; QoD dosing, 16 doses], epacadostat [32 doses], and pembrolizumab [1 dose]) at the level assigned or have a DLT will be considered evaluable for determining tolerability of the dose.

Individual subject dose reductions may be made based on events observed at any time during treatment with study drug; however, for the purposes of dose cohort escalation/de-escalation, expanding a dose cohort, and determining the MTD of the study drugs, decisions will be made based on events that are observed from the first day of study drug administration through and including the final day of Cycle 1 (Day 21) for Treatment Group A or Cycle 2 (Day 42) for Treatment Groups B and C. A lower MTD may subsequently be determined based on relevant toxicities that become evident after Day 21 (Treatment Group A) or Day 42 (Treatment Groups Band C).

Table 10: Definition of Dose-Limiting Toxicity

Toxicity

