
o!Unennatologic
 
 • Grade 4 (life-threatening) vomiting or diarrhea • Grade 4 electrolyte abnormality • Grade 4 systemic reaction • Any 2: Grade 3 no!Unematologic toxicity EXCEPT the following: 
 – Transient(72 hours) abno!mal laboratory values without associated clinically significant signs or symptoms. – ausea, vomiting, and diarrhea adequately controlled with medical therapy within 48 hours. – Grade 3 rash in the absence of desquamation, with no mucosal involvement, that does not require systemic steroids, and that resolves to Grade 1 within 14 days. – An event clearly associated with the underlying disease, disease progression, a concomitant medication, or comorbidity. – Asymptonnatic changes in lipid profiles. – Singular or nonfasting elevations in blood glucose (ie, blood glucose excursions will be considered toxicities if fasting blood glucose is elevated on 2 separate occasions). – Immtime-related adverse events of Grade 3 or higher that improve toGrade 1 in < 5 days by appropriate care or with corticosteroid therapy.

Hennatologic
 
 • 2: Grade 3 thrombocytopenia with clinically significant bleeding (requires hospitalization, transfusion of blood products, or other urgent medical intervention). • Grade 4 thrombocytopenia of any duration • Grade 4 neutropenia lasting > 3 days • 2: Grade 3 febrile neutropenia (absolute neutrophil cotmt < 1.0 x 10⁹/L and fever > 101°F/38.5°C). • Grade 4 neutropenia that does not recover toGrade 2 in3 days after interm!pting study dmg. • Grade 4 anemia not explained by underlying disease or some other concomitant disorder.

General
 
 • Subjects being unable to receive 2: 75% of study dmg doses during the DLT observation period because of toxicity, even if the toxicity does not meet DLT criteria defined above. 
ote:Exceptions include the DLT exclusions mentioned above.

MTD
 
 • 1 dose level below that at which 2: one-third of subjects in a palticular cohort has DLTs. Dose-limiting toxicity will be defined as the occull'ence of any of the toxicities in this table occUITing up to and including study Day 21.

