5.4.1.1.3. Procedures for Cohort Review and Dose Escalation

Telephone conferences will be scheduled by the sponsor with study investigators in order to review cohort-specific data and overall safety data, agree on dose escalation, adjudicate individual high-grade AEs as potentially dose-limiting, and guide other major study decisions.

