Repeat scan at 4 and 8 weeks shows SD, PR, or CR	Continue regularly scheduled imaging assessments every 9 weeks	Continue study treatment at the investigator's discretion	Continue regularly scheduled imaging assessments every 9 weeks	May restart study treatment if condition has improved and/or clinically stable per investigator's discretion

543. Procedures for Subjects Exhibiting Serotonin Syndrome

As noted in Section 1.8.1, there is a rare possibility that epacadostat could cause an increase in serotonin levels in the brain that might trigger SS (Boyer and Shannon 2005) when administered in combination with other serotonergic agents. This syndrome has been most closely associated with the use of MAOis, meperidine, tramadol, linezolid, or methylene blue; all of these agents are prohibited during the study. Selective SSRis and serotonin-norepinephrine reuptake inhibitors (SNRIs) are permitted during the study. The following procedures will be implemented if subjects exhibit the signs/symptoms of SS (Table 27), including tremor, hyporeflexia, spontaneous, ocular, or inducible clonus together with agitation, fever, diaphoresis, or muscle rigidity:

- Immediately interrupt epacadostat administration.
- Immediately interrupt any SSRI or SNRI administration.

- Provide appropriate medical management of the subject until all signs/symptoms are resolved (eg, IV fluids and/or sympathomimetic amines for hypotension, benzodiazepines for agitation, administration of 5-hydroxytryptamine antagonists such as cyproheptadine).
- If the subject chooses to remain in the study, restart treatment with epacadostat after the SSRI or SNRI has been discontinued no sooner than 5 half-lives have elapsed for the specific SSRI or SNRI in question and after resolution of signs/symptoms of SS. The SSRI or SNRI dosing MAY NOT be restarted.
- If the subject chooses to discontinue the study or must restart treatment with SSRI or SNRI, the subject should be scheduled for a follow-up visit. Selective serotonin reuptake inhibitor or SNRI treatment may be initiated 2 weeks after resolution of signs and symptoms of SS.

Table 27: Signs and Symptoms of Serotonin Syndrome

Tremor and hyporeflexia
Spontaneous clonus
Muscle rigidity, temperature > 38°C (100.4°F), and either ocular clonus or inducible clonus
Ocular clonus and either agitation or diaphoresis
Inducible clonus and either agitation or diaphoresis

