The occurrence of AEs should be sought by nondirective questioning of the subject during the screening process after signing the ICF and at each visit during the study. Adverse events may also be detected when they are volunteered by the subject during the screening process or between visits, or through physical examination, laboratory test, or other assessments. To the extent possible, each AE should be evaluated to determine:

- The severity grade (CTCAE Grade 1 to 4).
- Whether there is at least a reasonable possibility that the AE is related to the study treatment: suspected (yes) or not suspected (no).
- The start and end dates, unless unresolved at final follow-up.
- The action taken with regard to study drug.
- The event outcome (eg, not recovered/not resolved, recovered/resolved, recovering/resolving, recovered/resolved with sequelae, fatal, unknown).
- The seriousness, as per SAE definition provided in Section 8.3.1.

Unlike routine safety assessments, SAEs are monitored continuously and have special reporting requirements (see Section 8.3.2).

All AEs should be treated appropriately. If an AE is treated with a concomitant medication or nondrug therapy, this action should be recorded on Adverse Event form and the treatment should be specified on the Prior/Concomitant Medications or Procedures and Non-Drug Therapy form in the eCRF.

Once an AE is detected, it should be followed until it has resolved or until it is judged to be permanent; assessment should be made at each visit (or more frequently if necessary) of any changes in severity, the suspected relationship to the study drug, the interventions required to treat the event, and the outcome.

When the severity of an AE changes over time for a reporting period (eg, between visits), each change in severity will be reported as a separate AE until the event resolves. For example, 2 separate AEs will be reported if a subject has Grade 1 diarrhea, meeting the definition of an AE, that lasts for 3 days before worsening to a Grade 3 severity. The Grade 1 event will be reported as an AE with a start date equal to the day the event met the Grade 1 AE definition and a stop date equal to the day that the event increased in severity from Grade 1 to Grade 3. The Grade 3 event will also be reported as an AE, with the start date equal to the day the event changed in intensity from Grade 1 to Grade 3 and a stop date equal to the day that the event either changed severity again or resolved.

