APPENDIX E. PROTOCOL AMENDMENT SUMMARY OF CHANGES

Document	Date
Amendment (Version) 1:	18 JAN2016
Amendment (Version) 2:	08 JUL2016
Amendment (Version) 3:	20 OCT 2017
Amendment (Version) 4:	30AUG2018

Amendment 4 (30 AUG 2018)

Overall Rationale for the Amendment:

The primary purpose of this amendment is to 1) specify that scans to confirm disease progression should be conducted at least 4 weeks and no later than 8 weeks from the initial scans showing PD and 2) remove the disease assessment and survival follow up visits.

1. Synopsis; Section 4.4, Duration of Treatment and Subject Participation; Section 5.5.2, Withdrawal Procedures; Section 6, Study Assessments (schedule of assessment Tables 29, 31, 33, 35); Section 6.4.1, Safety Follow-Up; Section 6.4.2, Disease Status Follow-Up; Section 6.4.3, Survival Follow-Up; Section 6.5, End of Study; Section 7.6.1, Assessment of Disease According to Modified RECIST v1.1; Section 7.10.2, Data Collection for Survival Follow-Up

Description of change: Follow-up visits and contacts for disease assessment and survival will no longer be required. For Treatment Group A, reference to subject contact after the safety follow-up visit (42-49 days after EOT) have been revised. As of Amendment 4, Treatment Groups Band Care no longer applicable. No subjects have been or will be enrolled in these cohorts.

Rationale for change: Based on an External Data Monitoring Committee's (eDMC) analysis of the ECH0-301/KEYNOTE-252 Phase 3 melanoma clinical study, Incyte made a strategic decision to stop further enrollment in the INCB 24360-206 study. The eDMC analysis determined that the ECH0-301/KEYNOTE-252 clinical study did not meet the prespecified endpoint of improvement in PFS for the combination of pembrolizumab and epacadostat compared to pembrolizumab and placebo. Of note, based on review of the safety analysis, the eDMC concluded that there were no safety concerns with the ECH0-301/KEYNOTE-252 investigational group compared to pembrolizumab alone. Data collection for disease assessment and survival follow-up is no longer required.

2. Section 5.4.2, Treatment After Initial Evidence of **Radiographic Disease Progression (including Table 26);** [REDACTED]

Rationale for change: This modification has been made per FDA request.

3. Synopsis; Section 4.1, Overall Study Design; Section 4.4, Duration of Treatment and Subject Participation; Section 5.2.3. 1, Description and Administration

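### The febrile-neutropenia DLT in Table 10 gives one strict fever limit in two units that do not agree (101°F is 38.33°C; 38.5°C is 101.3°F)

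*Protocol*

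**What the plan says.** Protocol Section 5.4.1.1 makes any Table 10 toxicity a DLT if it falls within the observation window (through Day 21 for Treatment Group A, Day 42 for Groups B and C). Under hematologic toxicities, Table 10 lists febrile neutropenia of Grade 3 or higher, with ANC below 1.0 x 10^9/L and "fever > 101°F/38.5°C".

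On assessment, the section says "All DLTs will be assessed by the investigator using the current CTCAE v4.03 criteria". It does not reproduce a CTCAE temperature. It also limits what may be set aside as a non-DLT to a short list: a clear alternative explanation, transient laboratory values without clinically significant signs or symptoms, and high-grade immune-related events that resolve quickly. Section 5.4.1.1.3 adds telephone conferences of sponsor and investigators, which among other things "adjudicate individual high-grade AEs as potentially dose-limiting".

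The SAP repeats the escalation rules (Section 3.1.2) and lists DLTs by dose level (Section 8.2.2), but gives no fever limit for a DLT. The > 38°C entries in Protocol Table 57 and SAP Table 13 flag notable vital signs and do not define DLTs.

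**The concern.** A DLT definition should give one answer for one reading. Here the limit is strict and is printed as though the two figures were the same temperature. They are not, so a site that reads the Celsius figure and a site that reads the Fahrenheit figure can classify the same event differently.

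The classification is operative. Under Protocol Section 4.1.1, one DLT among the first 3 subjects expands the cohort to 6, and two among 3 require de-escalation. In principle a single borderline call could change the size of a cohort or the next dose.

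**Working it through.** **Inputs.** The pair 101°F and 38.5°C from Protocol Table 10. For comparison, two other dual-unit limits in the protocol: the INCB059872 storage range in Section 5.2.5.3 and the serotonin-syndrome fever limit in Table 27 (Section 5.4.3).

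**Formulas.** C = (F − 32) × 5/9 and F = C × 9/5 + 32.

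**The plan's own pair.**
- 101°F: (101 − 32) × 5/9 = 38.33°C, which is 38.3 to one decimal and not 38.5.
- 38.5°C: 38.5 × 9/5 + 32 = 101.3°F, which becomes 101 only when rounded to the whole degree.
- Gap: 38.50 − 38.33 = 0.17°C; 101.3 − 101 = 0.3°F.

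**Which readings are affected**, in tenths of a degree on either scale:

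| Reading | Converted | > 101°F? | > 38.5°C? |
|---|---|---|---|
| 38.3°C | 100.94°F | no | no |
| 38.4°C | 101.12°F | yes | no |
| 38.5°C | 101.30°F | yes | no |
| 38.6°C | 101.48°F | yes | yes |
| 101.0°F | 38.33°C | no | no |
| 101.1°F | 38.39°C | yes | no |
| 101.2°F | 38.44°C | yes | no |
| 101.3°F | 38.50°C | yes | no |
| 101.4°F | 38.56°C | yes | yes |

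The two limits disagree for every temperature above 38.33°C up to and including 38.5°C: two tenth-degree Celsius readings and three Fahrenheit ones.

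**Comparison with other pairs in the protocol.**
- Storage, "between 2°C and 8°C (36°F-46°F": exact values are 2 × 9/5 + 32 = 35.6°F and 8 × 9/5 + 32 = 46.4°F, so this range is rounded to whole degrees.
- Table 27, "temperature > 38°C (100.4°F": 38 × 9/5 + 32 = 100.4°F, so this fever limit keeps the decimal and is exact.

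**If the printed figure were 38.3°C.** 38.3 × 9/5 + 32 = 100.94°F. No tenth-degree Celsius reading would be discordant. In Fahrenheit only 101.0°F would be, since it is 38.33°C (above 38.3°C) but is not above 101°F.

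**The case against.** The strongest reply is that this is rounding. 38.5°C is 101°F to the whole degree, and the storage range is rounded in the same way. Table 27 is a single exact pair and does not establish a house rule. That is a fair account of how the figure may have arisen, but it does not cure the text: once printed after a strict inequality, 101°F is a limit in its own right and classifies some readings differently.

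A second reply is that the digit may be wrong only in the text copy. Other characters in Table 10 are misread there, and the SAP does not reproduce the table, so no second copy confirms 38.5. The figure itself reads cleanly and nothing positively points to a misread 38.3, but the PDF should be checked before any change.

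A third reply is that fever is only one condition. The event must also be Grade 3 or higher with a low neutrophil count, the investigator and cohort review can settle individual cases, and another Table 10 criterion may apply (Grade 4 neutropenia lasting more than 3 days, or failure to receive 75% of doses because of toxicity). All of this narrows the practical exposure. It does not tell reviewers which of the two limits to apply, and doubt about units is not among the listed grounds for calling an event a non-DLT.

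A reader might infer that dose escalation in this trial was compromised, or that sites did classify events differently. The documents do not support either inference. Section 1.8.6 reports the azacitidine combination as well tolerated in Cohorts 1, 2A, 2B and 3, "with no DLTs observed to date in Part 1", and those are all the dose levels from the starting dose upward in Table 1. Appendix E records a "strategic decision to stop further enrollment" and states that Groups B and C enrolled nobody. No document mentions a borderline temperature.

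**Conclusion.** The inconsistency is real and small. Table 10 prints one DLT fever limit as two temperatures 0.17°C (0.3°F) apart, and neither document says which one governs. It is a unit-conversion inconsistency in a decision threshold. No sample size, power or error rate depends on it, and no escalation decision in this trial is shown to have been affected.

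Two assumptions carry the conclusion. The first is that the protocol PDF prints 38.5; if it prints 38.3, the pair agrees to one decimal and only a reading of exactly 101.0°F is discordant. The second is that the undated no-DLT statement in Section 1.8.6 still held when enrollment stopped. If a DLT was considered later, the band could matter only for a febrile-neutropenia event that peaked inside it.

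**What to change.** Confirm the digit in the protocol PDF. If it reads 38.5, print > 38.5°C (101.3°F) in Table 10. That pair converts exactly, so no reading can fall between the two units.

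If medical review prefers the lower and more conservative limit, state > 101°F as the governing value and mark 38.3°C as approximate. Printing 38.3°C as an equal alternative would leave 101.0°F discordant.

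The cost is one figure in one table, with no change to any analysis. The main benefit is to any later document that reuses Table 10. I would not propose a retrospective re-check. Peak temperature is not on the list that Section 8.1.2 introduces with "To the extent possible, each AE should be evaluated to determine", and the visit temperatures collected under Section 7.5.3 need not capture a peak.

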5.4.1.1.1. Management of Dose-Limiting Toxicities or Other Urgent Situations

In all cases, investigators may employ any measures or concomitant medications, after discussion with the sponsor (whenever possible), necessary to optimally treat the subject.

5.4.1.1.2. Follow-Up of Dose-Limiting Toxicities

Any DLT should be followed until it resolves to baseline or appears to have stabilized for a minimum of 4 weeks. During follow-up, subjects should be seen as often as medically indicated to assure safety.

5.4.1.1.3. Procedures for Cohort Review and Dose Escalation

Telephone conferences will be scheduled by the sponsor with study investigators in order to review cohort-specific data and overall safety data, agree on dose escalation, adjudicate individual high-grade AEs as potentially dose-limiting, and guide other major study decisions.

5.4.1.2. Criteria and Procedures for Dose Interruptions and Adjustments of Study Drug

Treatment with study drug may be delayed up to 2 weeks (14 days) to allow for resolution of toxicity. If only 1 of the 2 agents is suspected to be responsible for the toxicity, only the suspected agent should be held (while the other treatment continues). In some circumstances, it may be necessary to temporarily interrupt the combination as a result of AEs that may not have a cause attributable to a single drug or that may be the result of combined toxicity.

Subjects may resume treatment if no medical condition or other circumstance exists that, in the opinion of the investigator, would make further participation in the study unsuitable. The treating investigator should contact the sponsor to discuss the case of any subject whose treatment has been delayed for more than 14 days before restarting treatment with the study drugs.

Because subjects may enter the study with extensive pretreatment and/or severe bone marrow infiltration by the primary disease, these dose reduction rules are provided as guidelines (see [Table 15](#) through [Table 17](#)). Individual decisions regarding dose reduction should be made using clinical judgment and in consultation with the sponsor's medical monitor, taking into account relatedness of the AE to the study drug and the subject's underlying condition. Adverse events that have a clear alternative explanation or transient (≤ 72 hours) abnormal laboratory values without associated clinically significant signs or symptoms may be exempt from dose-reduction rules.

5.4.1.2.1. Pembrolizumab Dose Modifications

There will be no dose reductions of pembrolizumab allowed for the management of toxicities of individual subjects. Doses of pembrolizumab may be delayed for toxicity management.

5.4.1.2.2. Epacadostat Dose Modifications

[Table 11](#) describes epacadostat dose reductions that may occur due to any related AEs. Dose reductions should occur in a step-wise fashion from the initial starting dose of the cohort, and a maximum of 2 dose reductions of epacadostat are allowed for the management of an AE, regardless of the initial starting dose. If an AE recurs/does not return to baseline after the second

dose reduction of epacadostat, then the subject must permanently discontinue epacadostat. The lowest permissible dose of epacadostat is 25 mg BID. If a subject does not tolerate 25 mg BID, then the subject must permanently discontinue epacadostat.

Table 11: Epacadostat Dose Reductions

Dose Level
300mgBID
100mgBID
50mgBID
25 mgBID

5.4.1.2.3. Azacitidine Dose Modifications

Table 12 describes azacitidine dose reductions that may occur due to any related AEs. Dose reductions should occur in a step-wise fashion from the initial starting dose of the cohort, and a maximum of 2 dose reductions of azacitidine are allowed for the management of an AE, regardless of the initial starting dose. If an AE recurs/does not return to baseline after the second dose reduction of azacitidine, then the subject must permanently discontinue azacitidine. The lowest permissible dose of azacitidine is 50 mg. If a subject does not tolerate 50 mg, then the subject must permanently discontinue azacitidine.

Table 12: Azacitidine Dose Reductions

Dose Level
100mg
75mg
50mg

5.4.1.2.4. INCB057643 Dose Modifications

Table 13 describes INCB057643 dose reductions that may occur due to any related AEs. Dose reductions should occur in a step-wise fashion from the initial starting dose of the cohort, and a maximum of 2 dose reductions of INCB057643 are allowed for the management of an AE, regardless of the initial starting dose. If an AE recurs/does not return to baseline after the second dose reduction of INCB057643, then the subject must permanently discontinue INCB057643. The lowest permissible dose of INCB057643 is 4 mg. If a subject does not tolerate 4 mg, alternative dose schedules may be evaluated.

Table 13: INCB057643 Dose Reductions

Dose Level
12mgQD
8mgQD
4mgQD

